7.5 Multicenter Clinical Trials

Multi-center study including up to 20 sites in the US.

7.6 Multiple Comparisons and Type I Error Rate Multiplicity adjustments

There is no need to adjust for multiplicity in this Phase II study.

7.7 Covariates and Prognostic Factors

There are no pre-planned covariates analyses of the data from this study.

7.8 Stratification Factors

Donor source (i.e., HLA-Matched Unrelated Donor (MUD) vs HLA-Mismatched Related Donor (MRD)) will be used as a stratification factor in this study.

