# LIST OF ABBREVIATIONS

Abbreviation	Term
AE	Adverse Event
ALT	Alanine Transaminase
AML	Acute Myeloid Leukemia
ANC	Absolute Neutrophil Count
AST	Aspartate Transaminase
AUC	Area Under Curve
°C	Celsius
CBC	Complete Blood Count
CCR5	C-C chemokine receptor type 5
CFR	Code of Federal Regulations
СНО	Chinese Hamster Ovary
cm	Centimeter
$C_{max}$	Maximal Concentration
CNS	Central Nervous System
CRF	Case Report Form
CR	Complete remission
CRO	Contract Research Organization
CS	Clinically Significant
CTCAE	Common Terminology Criteria for Adverse Events
DLCO	Lung Diffusion Capacity Testing
DMC	Data Monitoring Committee
DNA	Deoxyribonucleic acid
DO	Doctor of Osteopathic Medicine
ECG	Electrocardiogram
ECOG	Eastern Cooperative Oncology Group
eCRF	Electronic Case Report Form
$\mathbf{E}_{max}$	Maximum drug effect
et al	et aliae; Latin for "and others"
°F	Fahrenheit
FDA	U.S. Food and Drug Administration
FDP	Fixed Dose Procedure
FU	Follow-Up
GCP	Good Clinical Practice

[figure not shown]
CONFIDENTIAL Page 33 of 108

Abbreviation	Term
GI	Gastrointestinal
GVHD	Graft Versus Host Disease
НСТ	Hematopoietic Cell Transplantation
Hb	Hemoglobin
HBsAg	Hepatitis B surface Antigen
НСТ	Hematocrit
HEENT	Head, Ears, Eyes, Nose, and Throat
HIPAA	Health Insurance Portability Accountability Act
HIV	Human Immunodeficiency Virus
HLA	Human Leukocyte Antigen
IA	Interim Analysis
IB	Investigator's Brochure
IBMTR	International Bone Marrow Transplant Registry
ICF	Informed Consent Form
ICH	International Conference on Harmonization
iDMC	Independent Data Monitoring Committee
i.e.	id est; Latin for "that is"
IEC	Independent Ethics Committee
IND	Investigational New Drug
INR	International Normalized Ratio
IP	Investigational Product
IRB	Institutional Review Board
ISR	Injection Site Reactions
ITT	Intent-to-treat
IV	Intravenous
LAR	Legally Acceptable Representative
LDH	Lactate dehydrogenase
LPN	Licensed Practical Nurse
LVEF	Left Ventricular Ejection Fraction
LVN	Licensed Vocational Nurse
mAb	Monoclonal Antibody
MD	Doctor of Medicine
MDS	Myelodysplastic Syndromes
MedDRA	Medical Dictionary for Regulatory Activities
mg	Milligram

[figure not shown]
CONFIDENTIAL Page 34 of 108

Abbreviation	Term
mL	Milliliter
mm	Millimeter
MRD	HLA-Mismatched Related Donor
MUD	HLA-Matched Unrelated Donor
MUGA	Multi Gated Acquisition Scan
MW	Molecular Weight
NCS	Not Clinically Significant
NMDP	National Marrow Donor Program
NP	Nurse Practitioner
PA	Physician Assistant
PBSC	Peripheral Blood Stem Cell
PI	Principal Investigator

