#### 3.3 ELIGIBILITY CRITERIA

#### 3.3.1 Inclusion Criteria

Subjects must meet all of the following criteria to be included in the study:

- 1. Patients diagnosed with AML or MDS per below:
  - Patients with a history of histologically or pathologically confirmed diagnosis of AML and < 5% blasts in the peripheral blood or bone marrow (per bone marrow aspiration and/or biopsy within 6 weeks prior to screening) scheduled to undergo allogeneic stem-cell transplantation
  - Patients with a histologically or pathologically confirmed diagnosis of MDS with
     10% blasts in the bone marrow (per bone marrow aspiration and/or biopsy within 6 weeks prior to screening) scheduled to undergo allogeneic stem-cell transplantation
- 2. Eastern Cooperative Oncology Group (ECOG) performance status score  $\leq 2$
- 3. Patients must have normal organ function as defined below:
  - Myeloablative allogeneic HCT:
    - Males and females, age  $\ge 18$  and  $\le 65$  years of age
    - Total bilirubin  $\leq$  2 mg/dL (except in patients with Gilbert's Syndrome)
    - AST/ALT  $\leq$  3 times institutional upper limit of normal (except in patients with leukemic infiltration of liver)
    - Serum creatinine  $\leq 2 \text{ mg/dL}$  and creatinine clearance  $\geq 60 \text{ ml/hr}$
    - Diffusing capacity of the lung for carbon monoxide (DLCO) > 50% predicted with no symptomatic pulmonary disease
    - Cardiac ejection fraction ≥ 50%. If between 40-49% a cardiology consult is required

CONFIDENTIAL Page 50 of 108

[figure not shown]
- Clinically normal resting 12-lead ECG at screening visit or, if abnormal, considered not clinically significant by the PI
- 4. Patients must have a reasonable expectation of  $\geq 6$  months survival
- 5. The donor-recipient HLA match criteria required for participation in this protocol are not research subjects in this study and they must meet criteria as National Marrow Donor Program (NMDP) donors. Procedures for selection of donors and stem cell dose will follow FDA requirements for Blood Products (21 CFR 640) and Human Cellular and Tissue Based Products (21 CFR 1271). The standard institutional practices for stem cell transplants also will be followed. The donors are:
  - o HLA-Identical Sibling (6/6): Minimal typing necessary is serologic typing for class I (AB) and molecular typing for class II (DRB1)
  - Matched Unrelated Donor (8/8): Molecular identity at HLA A, B, C and DRB1 by high-resolution typing

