  - o Matched Related and Unrelated Donor (7/8): high-resolution molecular typing at the following loci is required: HLA A, B, C and DRB1
- 6. Both male and female patients and their partners of childbearing potential must agree to use appropriate birth control methods (birth control pills, barriers, or abstinence) throughout the study duration (excluding women who are not of childbearing potential and men who have been sterilized). Females of childbearing potential must have a negative serum pregnancy test at Screening visit and negative urine pregnancy test prior to receiving the first dose of study drug.
- 7. Patients must understand and voluntarily sign an informed consent form

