#### 7.12 RANDOMIZATION

Subjects who are eligible to participate in the trial will be randomized to one of the treatment groups via IWRS (Interactive Web Based Randomization System) at the T1 Visit prior to IP administration. The randomization will be central and will use mixed block size of 2 and 4 with a 1:1 ratio of Active Treatment to Control Treatment to ensure even distribution of Active and Control subjects. A randomization plan that details the stratification and randomization will be developed.

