## 8.4 RANDOMIZATION, STRATIFICATION AND BLINDING

This is a double-blind, multi-center randomized clinical trial. The randomization will be central and will use mixed blocks of 2 and 4 with a 1:1 ratio of Active to Control to ensure even distribution of Active and Control subjects.

Randomization will be conducted via a Web based system, and the process for the blinding requirements will be outlined in the study randomization plan. To decrease the effect of HLA-Matched Unrelated Donor (MUD) vs HLA-Mismatched Related Donor (MRD) as a confounding factor in this study, the donor source will be used as a stratification factor. This stratification will allows us to achieve a balanced randomization scheme with more reliable interpretation.

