8.2.1 Primary Endpoint

The primary efficacy endpoint for this study is the incidence of \geq Grade II acute GVHD by Day - 100.

Chi-square/ Fisher's exact test will be used to compare the primary endpoint between the treatment groups.

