8.2.2.6 GVHD-free survival (GFS)

GFS will be defined as the elapsed time between the date of transplant until GVHD related death. Duration of GVHD-free survival will be measured as in Section 7.9.7.

GVHD-free survival will be compared between the treatment groups using Log-rank test and Kaplan-Meier methods will be used to depict the survival curves.

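### The printed donor-source strata leave out eligible donor types, and neither the primary test nor the GFS log-rank uses the factor the trial randomises by

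*SAP*

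**What the plan says.** Protocol 8.4 names the contrast "HLA-Matched Unrelated Donor (MUD) vs HLA-Mismatched Related Donor (MRD) as a confounding factor in this study" and makes donor source the randomisation stratum in order to reduce that confounding. SAP 2.4.2 repeats this, and SAP 7.8 restates it: "Donor source (i.e., HLA-Matched Unrelated Donor (MUD) vs HLA-Mismatched Related Donor (MRD)) will be used as a stratification factor in this study". The protocol's abbreviation list also expands MRD as "HLA-Mismatched Related Donor".

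Inclusion criterion 5 (Protocol 3.3.1) lists the eligible donors. The first is "HLA-Identical Sibling (6/6): Minimal typing necessary is serologic typing for class I (AB) and molecular typing for class II (DRB1"). The second is a matched unrelated donor at 8/8. The third is "Matched Related and Unrelated Donor (7/8): high-resolution molecular typing at the following loci is required".

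Protocol 7.12 defers the detail: "A randomization plan that details the stratification and randomization will be developed". That plan is not among the documents.

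For the analysis, SAP 8.2.1 says "Chi-square/ Fisher's exact test will be used to compare the primary endpoint between the treatment groups", and SAP 8.2.2.6 says "GVHD-free survival will be compared between the treatment groups using Log-rank test". Neither mentions strata. SAP 7.7 and Protocol 8.6.3 plan no covariate analyses.

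**The concern.** There are two linked problems.

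First, a stratification factor has to place every randomised subject in exactly one level. Here the printed levels combine two attributes, relatedness and HLA match, and name only two of the four combinations. A donor type without a level has no assured balance between arms unless the randomization plan supplies one, and the protocol and SAP give the analyst no stratum for it.

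Second, the plan calls donor source a confounder and constrains the randomisation by it, then leaves it out of every analysis without giving a reason. If GVHD risk differs between strata, a test that ignores them uses a variance that is too large for the design. The test becomes conservative and power falls. With 60 subjects there is little to spare.

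**Working it through.** **Part 1: donor types against strata.** The status of a 7/8 donor decides the result, so both readings are shown.

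| Eligible donor (inclusion 5) | Stratum if 7/8 counts as matched (inclusion 5's own label) | Stratum if 7/8 counts as mismatched |
|---|---|---|
| 6/6 HLA-identical sibling | none | none |
| 8/8 unrelated | matched unrelated | matched unrelated |
| 7/8 related | none | mismatched related |
| 7/8 unrelated | matched unrelated | none |

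Under either reading applied consistently, two of the four types have no stratum. Under the first reading the mismatched-related stratum has no eligible donors at all. If *Mismatched* is a slip for *Matched*, and 7/8 counts as matched, a related versus unrelated split covers all four types. The word is, however, spelled out in Protocol 8.4, the abbreviation list, SAP 2.4.2 and SAP 7.8, so a reader cannot simply assume a slip.

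**Part 2: cost of ignoring the stratum.**

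*The plan's own figure.* SAP section 4 assumes 50% versus 15% with 30 per arm. The Wald interval is 0.35 ± 1.96 × √(0.5×0.5/30 + 0.15×0.85/30) = 0.35 ± 0.22, that is 0.13 to 0.57 with width 0.44. This reproduces the SAP.

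*Inputs.* There are 30 per arm, allocated 1:1 (SAP section 4). The test is two-sided at 5%. Protocol 8.7 prints the level as 0.05%; 5% is assumed here to agree with the SAP's 95% CI. The odds ratio implied by 50% versus 15% is (0.15/0.85)/(0.50/0.50) = 0.176; 0.25 is added as a weaker effect. The documents give no GVHD risk or share by donor stratum, only an overall 40-60%, so the stratum risks and shares below are assumptions.

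*Method.* Exact enumeration with 15 per arm in each of two strata (16⁴ = 65,536 outcome tables), a common odds ratio and no continuity correction. The unstratified statistic is the pooled two-proportion z. The CMH statistic is |Σ(x_h − t_h/2)| / √Σ{m_h² t_h(2m_h − t_h) / [(2m_h)²(2m_h − 1)]}, where, in stratum h, x_h is control events, t_h is total events and m_h is subjects per arm.

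| Control risk by stratum | Size: chi-square / CMH | Power at OR 0.176 | Power at OR 0.25 |
|---|---|---|---|
| 50% / 50% | 5.2% / 5.2% | 84.7% / 84.9% | 69.2% / 69.5% |
| 40% / 60% | 4.7% / 4.9% | 83.1% / 84.2% | 66.7% / 68.3% |
| 35% / 65% | 4.2% / 4.9% | 80.7% / 83.3% | 63.3% / 67.0% |
| 30% / 70% | 3.4% / 5.0% | 76.8% / 81.7% | 58.0% / 64.8% |

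The gain at 40/60 is 84.2 − 83.1 = 1.1 points (OR 0.176) and 68.3 − 66.7 = 1.6 points (OR 0.25). At 30/70 it is 4.9 and 6.8 points.

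*Unequal strata.* With 20 and 10 per arm, either way round, the gain is 0.6 to 1.3 points at 40/60 and 2.5 to 6.1 at 30/70. With 27 and 3 per arm and the small stratum at higher risk, it is 0.5 to 0.9 and 2.2 to 2.6 points. With the small stratum at lower risk it is under 0.3 points. CMH lost no power in any of these cases.

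**The case against.** The strongest reply on the strata is that the protocol delegates their definition to a separate randomization plan, which may assign every donor correctly. The printed text would then be a labelling slip. That is possible, and it limits what can be said about balance. It does not remove the contradiction between the strata and the eligibility criteria in the two documents the analyst works from. It can also be argued that a 7/8 unrelated donor belongs in the matched unrelated stratum, because inclusion 5 calls 7/8 matched. On that label, though, the 7/8 related donor loses its stratum instead.

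On the analysis, the unstratified tests are valid and their lack of adjustment is declared. The trial is a proof of concept with no power calculation, and the gain is small unless donor types differ widely in risk; the 5 to 7 points need an assumed 30% versus 70%. All of this stands, and it is why the point is an improvement and not the correction of an invalid test.

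Two further remarks are fair. The SAP does not say when chi-square or Fisher applies, and at 50% versus 15% that choice alone moves exact power from 84.7% to 77.7%, more than stratification does at the same effect. No calculation supports the log-rank change. GFS events are GVHD-related deaths only, may be few, and a stratified log-rank uses only within-stratum comparisons. Its case rests on consistency with the design.

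**Conclusion.** The concern holds. The text alone shows that 6/6 siblings have no printed stratum and that the 7/8 types cannot both be placed under one consistent reading. It also shows that no analysis uses donor source. Whether balance was actually affected cannot be judged without the randomization plan.

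The statistical cost is conservatism and lost power, not false positives. With equal strata it is about 0.2 points at equal risks, 1 to 2 points at 40/60 and 5 to 7 at 30/70, where the unstratified chi-square has a true size of 3.4%. These figures assume two strata, a common odds ratio and a 5% level. The change should be made, because it costs no power in the cases examined and settles in advance how subjects are assigned to strata in the analysis.

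**What to change.** 1. **Labels.** Bring Protocol 8.4, the abbreviation list and SAP 2.4.2 and 7.8 into line with inclusion 5, so that every eligible donor type falls in exactly one of a few levels. If enrolment has begun, leave the randomisation system unchanged, document how each type was assigned, and analyse by the strata actually used.
2. **Primary test.** In SAP 8.2.1, name a CMH test by donor source as the single primary test, with the Mantel-Haenszel risk difference and 95% CI. The risk difference is the quantity SAP section 4 uses to describe 60 subjects. Keep the unstratified test as a sensitivity analysis, and state in advance how a sparse or empty stratum is handled.
3. **GFS.** Stratify the log-rank in SAP 8.2.2.6 by the same factor, with a matching rule for sparse strata because events may be few.
4. **Consistency.** Amend SAP 7.7 to agree.

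Before enrolment the cost is wording and system labels. After enrolment it is documentation and SAP text, completed before database lock. The drawbacks are small strata in a trial of 60 and little gain if donor types carry similar GVHD risk.

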7.9 Standard Calculations

7.9.1 Age

Age will be calculated as the number of completed years between the date of informed consent and the subject's birth date.

Age (years) = integer of [(date of informed consent – date of birth)/
$$365.25+0.5$$
]

7.9.2 Height

For summary purposes height will be expressed in centimeters. Entries made in inches will be converted to centimeters using the formula noted below.

Height (cm) = Height (in)
$$*2.54$$

7.9.3 Weight

For summary purposes weight will be expressed in kilograms. Entries made in pounds will be converted to kilograms using the formula noted below.

Weight (kg) = Weight (lb)/
$$2.2046$$

7.9.4 Body Mass Index (BMI)

BMI will be calculated using height (in cm) and weight (in kg) according to the formula noted below.

BMI
$$(kg/m^2)$$
 = weight $(kg) / [[height (cm)/100]^2]$

7.9.5 Definition and Duration of Platelet Recovery

Platelet recovery will be defined as post-transplant increase in platelet levels to greater than $20,000/\mu$ L on two consecutive counts at least 2 days apart. If no platelet transfusion is given on or between the days of the two counts, the second platelet count should be at least as high as the first.

Duration of platelet recovery will be defined as the difference between the date of transplant and the date of the first eligible count of the two consecutive counts.

Duration of Platelet Recovery = (Date of first eligible count – Date of transplant) +1

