#### 7.11.1 Routine CBC

- Includes hemoglobin, hematocrit (HCT), red blood cell (RBC) count, white blood cell (WBC) count, WBC differential count (%), absolute neutrophils count (ANC) and platelets count.
  - Note: Platelet recovery will be defined as post-transplant increase in platelet levels to greater than 20,000/µL on two consecutive counts at least 2 days apart, if no platelet transfusion is given on or between the days of the two counts and the second platelet count is at least as high as the first. The date of platelet recovery will be defined as the day of the first eligible count per above. Neutrophil

CONFIDENTIAL Page 73 of 108

recovery will be defined as an increase in absolute neutrophil count (ANC) to greater than  $500/\mu$ L on 2 consecutive days. The date of neutrophil recovery will be defined as the day of the first count above the threshold.

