#### 8 STATISTICAL CONSIDERATIONS

This section presents general information about statistical considerations and concepts such as randomization, sample size, and a brief discussion on analysis methodology, as well as some data conventions. Detailed descriptions of the statistical analysis methods and data conventions that will be used in this study will be in a separate document; i.e., the Statistical Analysis Plan (SAP).

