1. INTRODUCTION

This Statistical Analysis Plan describes the planned analyses and reporting for the clinical trial protocol PRO 140_CD03_GVHD, sponsored by CytoDyn Inc. The reader of this Statistical Analysis Plan (SAP) is encouraged to review the complete protocol and amendments as this plan contains only a limited overview of protocol information. The main objective of this plan is to provide details pertaining to statistical methodology, data conventions, and processes used for the analysis of data from this trial.

The format and content of this Statistical Analysis Plan are structured to provide sufficient detail to meet the requirements specified by the International Conference on Harmonization (ICH) E9: Guidance on Statistical Principles in Clinical Trials. All work planned and presented in this Statistical Analysis Plan will follow the ethical guidelines published by the American Statistical Association (ASA).

The following documents and references [1-6], were reviewed in preparation of this Statistical Analysis Plan:

- Version 3.0, protocol 17 June 2016
- US Federal Register, Department of Health and Human Services, FDA, Guidance on Statistical Principles for Clinical Trials (1998)
- ASA Ethical Guidelines for Statistical Practice (1999)
- The Royal Statistical Society: Code of Conduct (1993)
- ICH Guidance on the Structure and Content of Clinical Study Reports (ICH E3, 1996)
- ICH Guideline on General Considerations for Clinical Trials (ICH E8, 1997)
- ICH Guidance on the Statistical Principles for Clinical Trials (ICH E9, 1997)

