8.2.2.4 Neutrophil and platelet count recovery

The number and percentages of subjects with neutrophil and platelet count recovery will be presented. The definition of neutophil and platelet count recovery is presented in Sections 7.9.5 and 7.9.6, respectively. Chi-square/ Fisher's exact test will be used to compare the incidence of neutrophil recovery and of platelet recovery between treatment groups.

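### SAP 7.9.5 loses the protocol's rule that a platelet transfusion disqualifies a pair of counts, so a transfused pair above 20,000/µL can be scored as platelet recovery

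*SAP*

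**What the plan says.** **Protocol 7.11.1 (Routine CBC)** defines platelet recovery in a single sentence. Counts must exceed 20,000/µL on two consecutive occasions at least 2 days apart, subject to a condition that begins "if no platelet transfusion is given on or between the days of the two counts and the second platelet count is at least as" and compares the second count with the first. The next sentence fixes the date: "The date of platelet recovery will be defined as the day of the first eligible count per above".

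**SAP 7.9.5** uses nearly the same words but puts a full stop after the 2-day spacing. A new sentence follows, beginning "If no platelet transfusion is given on or between the days of the two counts, the second platelet count should be at least", and it again compares the second count with the first. The duration then runs from transplant to "the date of the first eligible count of the two consecutive counts".

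**SAP 8.2.2.4** reports the number and percentage of subjects who recover and states that a chi-square or Fisher's "exact test will be used to compare the incidence of neutrophil recovery and of platelet recovery between treatment groups". For the definitions it sends the analyst to the SAP itself: "The definition of neutophil and platelet count recovery is presented in" Sections 7.9.5 and 7.9.6, respectively.

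**The concern.** In the protocol, freedom from transfusion is one of the requirements for recovery. In the SAP it has become the trigger for a different requirement, that the second count must not fall. No SAP sentence says what happens to a pair with a transfusion on or between the two days. Taken at its word, the SAP holds a transfused pair to a looser test than an untransfused one, although the transfusion itself may have produced the count.

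Neutrophil and platelet recovery is a named secondary efficacy endpoint, and its incidence is compared between arms. Two errors are possible:

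- **Proportion recovered.** A subject with a transfused pair above threshold and never an untransfused qualifying pair is counted as recovered when the protocol says not.
- **Date of recovery.** If a transfused pair comes first, recovery is dated too early. SAP 8.2.2.4 names no analysis of the duration. The general provisions of SAP 8.1 (Kaplan-Meier for time-dependent data, t-test or a non-parametric method for continuous data) could still bring it in.

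If one arm recovered more slowly and was transfused more, false recoveries would fall mainly in that arm and could hide the difference. That is reasoning about direction and not a computed effect.

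**Working it through.** The plan gives no figure to reproduce, so the check compares the two rules as logic and then applies them to the visit schedule.

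**Step 1. Write the rules.** Let A = both counts above 20,000/µL and at least 2 days apart; T = platelet transfusion on or between the two days; S = second count at least as high as the first.

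- Protocol 7.11.1: A and (not T) and S.
- SAP 7.9.5, literal: A and (if not T, then S), which equals A and (T or S).

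**Step 2. Compare them where A is true.**

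| Pair above threshold | Protocol | SAP, literal | SAP, silence treated as undecided |
|---|---|---|---|
| Not transfused, second not lower | accept | accept | accept |
| Not transfused, second lower | reject | reject | reject |
| Transfused, second not lower | reject | accept | open |
| Transfused, second lower | reject | accept | open |
| **Total** | 1 accept, 3 reject | 3 accept, 1 reject | 1 accept, 1 reject, 2 open |

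Where A is false, both rules reject all four combinations. Across all 8 combinations the protocol and the literal SAP agree in 6 and disagree in 2, and both disagreements are transfused pairs. With the protocol's conjunction put back into the SAP, they agree in 8 of 8. The cases are not weighted by how often they occur.

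**Step 3. Apply them to the schedule.** Both schedules of assessments place post-transplant CBCs on Days 7, 14, 21, 28, 42, 56, 70, 84, 98 and 112. That is 10 scheduled counts and 9 adjacent pairs: 3 with a nominal gap of 7 days and 6 with 14 days. A subject's recovery status changes only if at least one pair is transfused and above threshold and no pair qualifies without transfusion.

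**Step 4. Dating.** SAP 7.9.5 sets duration = (date of first eligible count − date of transplant) + 1. On nominal days, Day 14 gives 14 + 1 = 15, Day 21 gives 22 and Day 28 gives 29.

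- Days 14/21 transfused, Days 21/28 the first untransfused qualifying pair: 15 instead of 22, so 22 − 15 = 7 days early.
- Days 14/21 transfused, Days 28/42 the first untransfused qualifying pair: 15 instead of 29, so 29 − 15 = 14 days early.

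**Step 5. Two illustrations with assumed counts.** In both, Day 7 = 12,000, Day 14 = 32,000 and Day 21 = 24,000, with a transfusion strictly between Days 14 and 21.

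- Day 28 = 26,000 and Day 42 = 60,000, untransfused: the protocol gives a duration of 22, the literal SAP 15.
- Day 28 = 15,000 and Day 42 = 18,000: on these counts the protocol gives no recovery, while the literal SAP gives recovery at 15.

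**The case against.** **A transcription slip.** The strongest defence is that SAP 7.9.5 is a garbled copy of the protocol. Almost every word survives, and the platelet rule dates recovery from an *eligible* count, whereas the neutrophil rule in SAP 7.9.6 dates it from the first count above the threshold. *Eligible* therefore seems to mean more than the threshold, and on that reading the SAP matches the protocol: 1 accept, 3 reject. This probably explains the cause, but it does not supply the missing rule. The protocol ties *eligible* back to its preceding sentence, where the transfusion condition stands. The SAP drops that tie, and the non-decrease test for untransfused pairs is enough to give the word a meaning.

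**The protocol governs.** SAP 1 encourages the reader to consult the full protocol and calls its own account of it limited. Yet Protocol 8 says that detailed methods and "data conventions that will be used in this study will be in a separate document", namely the SAP. SAP 1 agrees: "The main objective of this plan is to provide details pertaining to statistical methodology, data conventions, and processes used for the analysis of data". SAP 8.2.2.4 then points to the SAP's own sections. Neither document says which prevails, so precedence is unsettled and cannot be relied on to repair the definition.

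**Small reach.** This is one component of one of six secondary efficacy endpoints, in a 60-subject study sized by clinical judgment. The four-case tally is not an effect size. The 9 pairs leave out CBCs at unscheduled visits. The neutrophil rule's two consecutive days also presuppose counts outside the weekly and two-weekly schedule. With denser counts, the 7- and 14-day dating errors could be shorter. All of this stands, and it limits the weight of the point without removing it.

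**Conclusion.** The concern holds. Followed as written, SAP 7.9.5 accepts two kinds of pair that Protocol 7.11.1 rejects, and no other SAP section restores the exclusion. Even if the SAP's silence is treated as undecided, those two kinds of transfused pair are still not excluded. A programmer could implement either rule and defend it from the documents.

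The result can overstate the proportion with platelet recovery and can date recovery early. The size and direction of any between-arm effect cannot be computed, because the documents give no transfusion or platelet recovery rates. The dating figures rest on nominal visit days and assumed patients. The primary endpoint and the sample size are untouched. This should be corrected before analysis because the affected rule feeds a planned between-arm test and the correction is simple.

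A clerical point in the same place carries no weight of its own: the cross-reference in SAP 8.2.2.4 is reversed, sending neutrophil recovery to the platelet section and platelet recovery to the neutrophil section.

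**What to change.** 1. In SAP 7.9.5, restore the joint condition of Protocol 7.11.1. Recovery requires two consecutive counts above 20,000/µL at least 2 days apart, no platelet transfusion on or between those days, and a second count at least as high as the first. Define the eligible count as the first count of a pair that meets all of these conditions.
2. In SAP 8.2.2.4, correct the cross-reference: neutrophil recovery to 7.9.6, platelet recovery to 7.9.5.

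If the departure from the protocol was intended, the SAP should say so and give the reason.

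The cost is SAP wording only, with no change to the schedule or the endpoints. The protocol's own rule already needs transfusion dates, and Protocol 7.5 records medications and therapies with start and stop dates. This assumes that platelet transfusions are entered there, which is worth confirming before the derivation is programmed.
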